medications for the last 28 days, including treatment-naive subjects, must have ≥ 1 day between their screening visit and Visit 2 (Baseline).

At Visit 2, baseline IOP will be measured for both eyes at 8:00 (± 60 min), 12:00 (± 60 min) and 16:00 (± 60 min). The study eye will be the eye that qualifies per eligibility criteria at Visit 2. If both eyes meet the eligibility criteria, the eye with the higher diurnal IOP at Visit 2 will be designated as the study eye. If both eyes meet the eligibility criteria and have the same mean diurnal IOP at Visit 2, the right eye will be designated as the study eye. Both eyes should be treated with the study medication for the duration of the study even if only one eye is eligible per IOP inclusion criteria.

Treatment Period (6 weeks):

Approximately 100 eligible subjects will be randomized to either DE-117 0.002% QD in the evening and vehicle QD in the morning or DE-117 0.002% BID in a 1:1 ratio. Subjects will be treated for 6 weeks with scheduled Visits 2, 3 and 4 (Baseline, Week 2 and Week 6).

At Visit 2 (Baseline), subjects will be instructed to instill their first dose of study medication (study eye drops) as per their assigned/randomized study treatment at 20:00 (± 60 minutes) that same evening. The next day, subjects will subsequently dose their assigned study medication at 08:00 (± 60 minutes) and 20:00 (± 60 minutes). At each scheduled follow-up visit, subjects will instill their morning dose of study medication/eye drops following the 08:00 IOP measurement at the investigative site (the doctor's office).

IOP will be measured at 08:00, 12:00 and 16:00 (± 60 minutes). At these scheduled visits, BCVA and slit-lamp biomicroscopy will be performed just prior to the 08:00 IOP measurement. Ophthalmoscopy (fundus examination) will be performed after 16:00 IOP measurement.

Pharmacogenomics/Genomics:

Subjects who consent to the optional pharmacogenomics/genomics laboratory study will provide a blood sample for future testing. The purpose of this exploratory research is to identify possible genetic markers associated with the study medication(s) and/or ocular conditions.

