6.2.2. Study Medication Administration

Subjects will instill one drop of study medication in each eye at approximately 20:00 (± 60 min) and 8:00 (± 60 min) daily for a total of 6 weeks.

Each subject will be instructed to instill one drop of study medication from bottle labeled “evening” in each eye at 20:00 and one drop of study medication from bottle labeled “morning” in each eye at 08:00, starting the evening of Visit 2 (Baseline, Day 1) through the morning before Visit 4 (Week 6).

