- An interim safety visit during the washout period (mid-washout visit: Visit 1a) may be performed if, in the investigator's opinion, a subject's IOP may be of concern during the washout period. If subjects are treated with a topical CAI during the washout period, a mid-washout visit (Visit 1a) is recommended.
- The eligibility visit (Visit 2) will be scheduled at the end of the washout period for those subjects on prior IOP-lowering medications.
- Subjects who have not used an IOP-lowering medication for the last 28 days, including treatment-naive subjects, will need a wait period of \geq 1 day before their Visit 2 (Baseline, Day 1).

- If a subject does not require washout from an IOP-lowering medication, but they use contact lenses in either eye, they will need a wait period of \geq 2-3 weeks (2 weeks for soft contact lens wearers, and 3 weeks for rigid contact lens wearers) with no contact use before their Visit 2 (Baseline, Day 1).
- Schedule the eligible subject to return for Visit 2 (Baseline, Day 1) after the required wait/washout period.
- A subject who does not meet eligibility criteria or will not otherwise continue in the study is considered a screen failure.

8.1.2. **Visit 1a (Optional, Washout Period)**

- Visit 1a is an interim safety visit (referred to as mid-washout visit) that may be performed during the washout period if, in the Investigator's opinion, a subject's IOP causes any safety concern during washout period.
- Update concomitant medications and procedures/therapies.
- Query the subject regarding AEs.
- As per the SoA ([Table 3](#)) and Procedures of Assessments ([Section 8.2](#)), perform the following procedures or assessments (all ophthalmic procedures to be performed in both eyes):
 - BCVA (prior to IOP measurement)
 - Biomicroscopy (prior to IOP measurement)
 - IOP

8.1.3. **Visit 2 (Baseline, Day 1)**

- Update concomitant medications and procedures/therapies.
- Confirm the subject has complied with the required wait/washout period for ocular hypotensive medication(s), or contact lenses use, if required.
- Query the subject regarding AEs.
- Obtain urine and perform urine pregnancy test, if the subject is a female of child-bearing potential.
- As per the SoA ([Table 3](#)) and Procedures of Assessments ([Section 8.2](#)), perform the following procedures or assessments immediately before the 08:00 IOP measurement (all ophthalmic procedures to be performed in both eyes):
 - BCVA (prior to the 08:00 IOP measurement)

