 - If more than 10 letters in BCVA were lost compared to the screening visit, then refraction should be performed again.
 - Biomicroscopy (prior to the 08:00 IOP measurement)
- Perform IOP measurement at 08:00 (± 60 min).

- If subject meets the 08:00 IOP eligibility requirements, schedule additional IOP measurements at 12:00.
- Perform IOP measurement at 12:00 (± 60 min).
 - If subject meets the 08:00 and 12:00 IOP eligibility requirements, schedule additional IOP measurements at 16:00
- Perform IOP measurement at 16:00 (± 60 min).
- Perform ophthalmoscopy in both eyes after the 16:00 IOP measurement.
- Perform final review of eligibility criteria after the 16:00 IOP measurement and ophthalmoscopy. The subject will then be randomized, via Interactive Response Technology (Medidata Balance/RTSM).
- A subject who does not meet eligibility criteria or will not otherwise continue in the study is considered a screen failure.
- After the subject has been randomized to a treatment arm, and assigned a treatment kit by Balance/RTSM, a study staff member must:
 - Dispense the assigned kit to the subject which will contain the following;
 - Two (2) bottle of study drug labeled “morning”
 - Two (2) bottle of study drug labeled “evening”
 - Give the subject verbal and written instructions for proper instillation of the study medication, the dosing schedule and regimen, and study medication storage.
- Instruct the subject to instill the study medicine daily, starting from this evening (“evening” dose) (20:00).
- Schedule the subject to return on Day 15 ± 2 for Visit 3 (Week 2).
- Inform the subjects they will be reminded of the morning and evening instillation of the study medication by phone call a few days before Visit 3.
- Remind the subjects that the morning dose of Visit 3 will be done at the clinic.
- Remind the subject to bring all used and unused study medication at Visit 3.

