4.1.2. Treatment Start and End Dates

Treatment start date is the date at which a randomized subject takes the first dose of the study medication.

Treatment end date is the date at which a randomized subject takes the last dose of the study medication. If the date of the last dose is missing, then

- The day before the Visit 4 (Week 6) will be considered the treatment end date for subjects who completed the study, and
- The day before the Exit Visit date will be used for subjects who prematurely discontinued from the study. If the Exit Visit date of a non-completer is not available, then the day before the last available visit date will be considered the treatment end date.

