4.3. Safety-Related Definitions

4.3.1. Adverse Event

Under Protocol 011712IN, an AE is defined as any untoward medical occurrence (e.g., sign, symptom, disease, syndrome, intercurrent illness) that occurs in a study subject, regardless of the suspected cause and regardless of timing of study medication administration. An *on-study* AE can occur any time after the date of informed consent through the last study visit. An AE will be considered as *treatment-emergent* if the AE occurred on or after the treatment start date up to the 2 days after treatment end date. Treatment-emergent AEs are a subset of on-study AEs. Both on-study and treatment-emergent AEs will be recorded, but only treatment-emergent AEs will be tabulated.

The severity of each AE will be graded by the Clinical Investigator as Mild, Moderate, or Severe.

Each AE will be classified into a system organ class (SOC) and coded to a preferred term (PT) using Medical Dictionary for Regulatory Activities (MedDRA), version 21.1 published in 2018.

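### The treatment-emergent rule goes by calendar date, so an adverse event that starts on Day 1 before the 20:00 first drop is tabulated as on-treatment (minor)

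*SAP*

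**What the plan says.** - **The rule.** SAP 4.3.1 counts an event as treatment-emergent if "the AE occurred on or after the treatment start date up to the 2 days after treatment end date". The same section restricts the tables to treatment-emergent events.
- **Its anchor.** SAP 4.1.2 defines the start date: it "is the date at which a randomized subject takes the first dose of the study medication". No clock time is attached.
- **When the first drop is taken.** Under Protocol 4.1, at Visit 2 "subjects will be instructed to instill their first dose of study medication (study eye drops) as per their assigned/randomized study treatment at 20:00" (±60 min), that same evening. Protocol 8.1.3 repeats this: "Instruct the subject to instill the study medicine daily, starting from this evening".
- **What comes before it that day.** Protocol 8.1.3 lists an adverse event query ("Query the subject regarding AEs"), visual acuity, slit-lamp examination, tonometry at 08:00, 12:00 and 16:00, and undilated ophthalmoscopy. Then: "Perform final review of eligibility criteria after the 16:00 IOP measurement and ophthalmoscopy". Randomization and dispensing follow.
- **What is collected.** Protocol 8.3.1 collects adverse events from the signing of consent, so events earlier on Day 1 are recorded. The onset-date format in SAP 6.2.3, Table 6, has no time part.

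**The concern.** The dose date and the dose are treated as the same boundary, and on Day 1 they are most of a day apart. Nothing in the SAP makes an exception for Day 1, compares onset time with dose time, or flags pre-dose events. An event that starts at 12:30 on Visit 2 carries the treatment start date and so enters the tables, although the subject has been neither randomized nor dosed.

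The safety objective is to compare BID with QD, and pre-dose events carry no information about that. The day's procedures act on the eye, with topical anaesthetic, fluorescein and corneal contact (Protocol 8.2.1.1), and SAP 9.1 tabulates ocular events separately. The table most exposed is therefore one that readers of this study will look at closely.

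**Working it through.** The plan states no figure on this point, so there is none to reproduce. The only design number needed is about 50 subjects per arm (SAP 3.3).

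**1. The timeline.** The earliest 08:00 tonometry is at 07:00, and the first drop falls between 19:00 and 21:00.
- Visit-day time before any drug but inside the window: 19 − 7 = 12 hours to 21 − 7 = 14 hours. Counted from midnight, it is 19 to 21 hours.
- Applanations in that time: 3 sessions × 2 eyes × at least 2 readings = at least 12.

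**2. The most that one subject can add.** 1/50 = 2 percentage points in an arm. SAP 9.1 counts a subject once per system organ class or preferred term, so a subject who has another event in the same row adds nothing to it.

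**3. Effect on the comparison.** Let q be the chance of a new pre-dose Day 1 event. It is the same in both arms because the event comes before randomization. Let p be the chance of any other event in the row, and take the two as independent (assumption). Then:
- observed incidence = p + q − pq = (1 − q)p + q
- observed difference = (1 − q) × (p_BID − p_QD)

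The documents give no value for q. The range below is an assumption.

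| q | Expected subjects per arm (50q) | Chance of at least one in 100 subjects, 1 − (1 − q)^100 | A 10-point difference becomes |
|---|---|---|---|
| 0.5% | 0.25 | 39% | 9.95 points |
| 2% | 1 | 87% | 9.8 points |
| 6% | 3 | 99.8% | 9.4 points |

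**4. Illustration** with assumed true incidences of 20% (BID) and 10% (QD), and q = 4%:
- BID: 0.96 × 0.20 + 0.04 = 23.2%
- QD: 0.96 × 0.10 + 0.04 = 13.6%
- Difference: 10 points becomes 9.6 points. Ratio: 2.0 becomes 23.2/13.6 = 1.7.
- Standard error of the difference: √[(0.20 × 0.80 + 0.10 × 0.90)/50] = 7.1 points becomes √[(0.232 × 0.768 + 0.136 × 0.864)/50] = 7.7 points.

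The absolute rates rise by 3.2 and 3.6 points, the noise rises a little, and the difference hardly moves. A ratio would shrink more, but the SAP plans no ratio for safety.

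**The case against.** Several points on the other side stand, and they limit the harm.

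- **Onset, not detection.** A reader might infer that anything found at the Visit 2 examination enters the tables. It does not: the rule turns on when the event occurred. A condition with onset before Day 1 stays out, and the Visit 2 slit-lamp grades are baseline scores (SAP 4.2.3), not automatically adverse events.
- **Few tonometry signs would be seen.** A reader might expect procedure-related staining or hyperaemia to be picked up routinely. The Visit 2 slit-lamp examination precedes the 08:00 tonometry, the event query is listed ahead of the eye procedures, and no later slit-lamp examination is scheduled until Week 2. Such signs would reach the form only by spontaneous report, later recall or incidental observation.
- **The comparison is not seriously diluted.** That reading is tempting because the safety objective is comparative, but the difference shrinks only by the factor (1 − q), and SAP 6 rules out statistical testing of safety measures.
- **Partial safeguards exist.** Suspected adverse reactions are tabulated separately and all events are listed (SAP 4.3.1.3 and 9.1). An event known to precede the first drop should be judged not related.
- **The same procedures recur** at Weeks 2 and 6, when events they cause are properly treatment-emergent. The change therefore affects only one of three tonometry days.

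It can also be argued that counting by date is deliberately inclusive, in line with SAP 6.2.3, where an event with a wholly missing onset date counts as treatment-emergent. This has less force. The SAP gives no such reason for the Day 1 rule, and its partial-date rule can work the other way: imputing the first of the month can move a post-dose event to before treatment. The fix below keeps the inclusive default where the order is unknown.

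**Conclusion.** The point holds as a small misclassification built into a stated rule. For a subject who takes the first drop on the evening of Visit 2, a new event starting earlier that day is tabulated as treatment-emergent although no study drug had been given. If the first dose is delayed to a later date, the same problem moves to the pre-dose hours of that date.

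The consequence is a slight, arm-independent inflation of absolute incidence, mainly ocular, with a little added noise. It affects no hypothesis test and no efficacy result. Its size cannot be fixed from the documents: the values of q used above are assumptions, and 2 percentage points per misclassified subject is a ceiling. The eCRF is not among the documents, so whether onset time is captured is unknown; even if it is, the SAP rule does not use it. Minor priority.

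**What to change.** Settle the following in SAP 4.3.1 before unmasking:

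1. Define treatment-emergent as onset after the first dose, keeping the existing end of the window.
2. For events dated on the treatment start date, class as pre-treatment those recorded at Visit 2 before dispensing, or flagged as starting before the first drop if the eCRF captures this.
3. Count Day 1 events of unknown order as treatment-emergent.

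The cost is a sentence or two in the SAP and one derivation, or one eCRF field if a flag has to be added. A few Day 1 events will still be assigned by default.

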4.3.1.1. Serious Adverse Event

Any AE is considered a SAE if it fulfills one or more of the following criteria:

- Death (i.e., the AE caused or led to death)
- Life threatening (i.e., immediately life-threatening)
- Inpatient hospitalization and/or prolonged hospitalization
- A persistent or significant disability/incapacity (i.e., the AE resulted in a substantial disruption of the subject's ability to carry out normal life functions)
- A congenital anomaly/birth defect in the offspring of a study subject who was exposed to study therapy prior to conception or during pregnancy
- Sight threatening event
- Other medically important event (e.g., requires medical or surgical intervention to prevent one or more of the listed above)

4.3.1.2. Ocular Adverse Event

An AE will be counted as an *ocular AE* if the Clinical Investigator selected “OD”, “OS”, or “OU” on the AE eCRF.

4.3.1.3. Suspected Adverse Reaction

An AE will be counted as a *suspected adverse reaction* (SAR) if the Clinical Investigator selected answered ‘Related’ to the AE eCRF question ‘Relationship to Study Drug’

4.3.1.4. Events of Special Interest

Events of special interest (ESI) in this study is defined as pregnancy, study medication administration error, or macular edema.

4.3.2. Safety Measures

Table 5 lists the safety measures to be evaluated for this study.

Table 5: Safety Assessments

| Safety Measures | Note |
|--|--|
| Slit-lamp biomicroscopy: anterior chamber cells anterior chamber flare lid hyperemia lid edema conjunctival (palpebral and bulbar) hyperemia conjunctival chemosis corneal edema corneal staining (with fluorescein) keratic precipitate anterior synechiae of iris posterior synechiae of iris | Anterior Chamber Cells will be graded as 0 = No cells, 0.5 = 1-5 cells, 1 = 6-15 cells, 2 = 16-25 cells, 3 = 26-50 cells, or 4 = > 50 cells. Anterior Chamber Flare will be graded as 0 = None, 1 = Faint, 2 = Moderate, 3 = Marked, or 4 = Intense. The other biomicroscopy parameters will be graded as 0 = None, 1 = Mild, 2 = Moderate, or 3 = Severe. |
| Ophthalmoscopy glaucomatous optic nerve cup to disc ratio retina macula choroid vitreous | Damage to optic nerve will be graded as 0 = None 1 = Mild, 2 = Moderate, 3 = Severe. Cup/disc ratio will be recorded with two decimal points (e.g., 0.80). Retina, macula, choroid, and vitreous will graded as 0 = Normal, 1 = Abnormal. |
| Best Corrected visual acuity | Best corrected visual acuity score measures the acuteness or clearness of corrected vision, with a range of [-0.30, 1.10] in logarithm of the minimum angle of resolution (logMAR) scale. A decrease in logMAR score indicates improvements in corrected visual acuity. |

4.4. Other Definitions

4.4.1. Prior and Concomitant Medications

Non-study medications will be categorized into prior medications and concomitant medications. Specifically, the *prior medication* is defined as any non-study medication taken and ended prior to the treatment start date. The *concomitant medication* is defined as any non-study medication taken concurrently while on the study medication, i.e., the treatment period of a concomitant medication taken by a subject's needs to overlap with his/her treatment period of the study medication.

5. STUDY POPULATION

5.1. Intent-to-Treat Population

The *Intent-to-Treat* (ITT) population will include all randomized subjects.

5.2. Safety Population

The *Safety* population will include all randomized subjects who received at least one dose of the study medication. Safety analyses will be performed using the Safety Population and summarized by actual treatment received.

5.3. Full Analysis Set

The *Full Analysis Set* (FAS) includes all randomized subjects who received at least one dose of the study medication and had at least one post-baseline IOP measurement of the study eye during the study. This will be the population used for efficacy analyses. Efficacy analyses will be performed using the FAS and summarized by treatment as randomized.

5.4. Per-Protocol Set

The Per-Protocol Set (PPS) is a subset of the FAS. It will be the analysis population for sensitivity analyses and will be summarized using treatment as randomized. Any subject affected by a significant protocol deviation that might affect the primary efficacy analysis will be excluded from the PPS. The PPS will be identified before the unmasking of treatment assignments.

Before the unmasking of treatment assignment, Santen's study team will review all protocol deviations, identify subjects with any protocol deviation that could impact the efficacy outcome, and determine whether or not to exclude the subject from the PPS.

6. GENERAL CONSIDERATIONS

All measures will be summarized by treatment (planned or actually received) descriptively. Continuous variables will be summarized using descriptive statistics such as number of observations (n), mean, standard deviation, median, minimum, and maximum. Categorical variables will be tabulated using frequency (n) and percent (%).

Analysis treatment groups are defined as DE-117 QD/Vehicle QD or DE-117 BID.

The statistical testing will be conducted at a significance level of 0.05 (2-sided) unless specified otherwise. No statistical testing will be conducted for safety measures.

All data manipulations, descriptive summaries, and statistical hypothesis testing will be performed using Statistical Analysis System (SAS) Version 9.4 or later.

6.1. Adjustments for Covariates

In general, baseline IOP score will be adjusted in the inferential analysis of each IOP endpoint. Detailed information on covariate adjustment is provided in [Section 8.1](#).

6.2. Handling of Missing Data

6.2.1. Efficacy Measure

For subjects with the use of any non-study IOP lowering therapy to lower IOP, unless otherwise specified, the IOP data collected after the non-study IOP lowering therapy will be censored (treated as missing) in efficacy analyses.

For each IOP endpoint, no imputation is needed for the analysis on observed cases using the mixed-effects model for repeated measures (MMRM).

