9.3.5. Handling of Missing Values

In the analysis of IOP, subjects with missing IOP value at any timepoint at Week2 or Week6 may be imputed using the last-observation-carried-forward (LOCF) approach for sensitivity analyses.

For medical events including AEs, completely or partially missing onset and resolution dates will be imputed in a conservative fashion to be detailed in SAP. The same rules will be followed to impute completely or partially missing start and end dates of non-study medications.

Unless otherwise specified, descriptive summaries will be based on observed cases. Additional details on handling of missing data will be provided in the SAP.

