9.3.6.1. Analysis of Primary Endpoint

The primary efficacy endpoint is IOP in the study eye at each specified timepoint (08:00, 12:00 and 16:00) at Week 2 (Visit 3) and Week 6 (Visit 4). For the primary analysis, a mixed-effect model for repeated measures (MMRM) will be carried out and least squares mean of the endpoint will be reported. The model will include treatment, visit, and treatment-by-visit interaction as fixed effects, baseline IOP as a covariate, and subject as a random effect.

Treatment differences between the DE-117 BID arm and QD arm will be reported for each time point along with p-values and 95% confidence intervals.

Analysis of covariance (ANCOVA) with missing data imputed by an LOCF approach will be used as sensitivity analyses.

In addition, plots of IOP measures versus analysis time/analysis visit will be provided.

9.3.6.2. Analysis of Secondary Efficacy Endpoints:

- Mean diurnal IOP in the study eye at Week 6 (Visit 4)
- Absolute change and percent change from baseline in IOP
- Absolute change and percent change from baseline in mean diurnal IOP
- Having a mean diurnal IOP reduction $\geq 20\%$, $\geq 25\%$, or $\geq 30\%$ from Baseline (Visit 2) at each post-baseline visit
- Having a mean diurnal IOP ≤ 18 mmHg at each post-baseline visit

Continuous secondary efficacy endpoints will be analyzed by a mixed-effects model for repeated measures (MMRM) using observed cases or analysis of covariance (ANCOVA) with missing data imputed by an LOCF approach. Binary secondary efficacy endpoints will be analyzed using Pearson's Chi-square test.

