4.2.5. IOP Response Endpoints and Response Rate

At each post-baseline visit (Week 2 or Week 6), the following response endpoints are defined:

- $\geq 20\%$ Reduction Response: the percent reduction from baseline in mean diurnal IOP in the study eye is at least 20%.
- $\geq 25\%$ Reduction Response: the percent reduction from baseline in mean diurnal IOP in the study eye is at least 25%.
- $\geq 30\%$ Reduction Response: the percent reduction from baseline in mean diurnal IOP in the study eye is at least 30%.
- ≤ 18 mmHg Response: the mean diurnal IOP in study eye is equal or below 18 mmHg.

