8.1.2. Sensitivity Analyses

To assess the robustness of the results from the primary analysis for primary endpoint, the sensitivity analysis will be performed using the same MMRM model on PPS. All the primary and sensitivity analyses will be implemented using SAS PROC MIXED. The main part of the SAS code for the specified MMRM analysis is provided in [Appendix 12.1](#).

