8.2. Analyses of Secondary Endpoints

For continuous secondary endpoints (mean diurnal IOP, change and percent change from baseline) at Week 2 (Visit 3) and Week 6 (Visit 4), MMRM and descriptive summaries will be performed. The MMRM will be the same as the one for primary endpoint.

For binary secondary endpoints, the responder rates will be summarized at each post-baseline visit. Pearson's Chi-square test will be used for comparison between DE-117 BID arm and QD arm.

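### SAP 8.2 gives no responder status or denominator for subjects whose IOP is censored after non-study IOP-lowering therapy; on the natural reading they leave the responder analysis instead of counting as failures

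*SAP*

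**What the plan says.** **Censoring rule.** SAP 6.2.1 deals with subjects who receive an added pressure-lowering treatment outside the study. It states: "unless otherwise specified, the IOP data collected after the non-study IOP lowering therapy will be censored (treated as missing) in efficacy analyses". No later section makes an exception. The section's only other statement on efficacy data is that the MMRM on observed cases needs no imputation.

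**Responder endpoints.** SAP 4.2.5 counts a response when "the percent reduction from baseline in mean diurnal IOP in the study eye is at least" 20%, 25% or 30%. A fourth endpoint is a mean diurnal IOP of 18 mmHg or lower. All four need a mean diurnal IOP at the visit.

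**Responder analysis.** SAP 8.2: "For binary secondary endpoints, the responder rates will be summarized at each post-baseline visit". The arms are compared by Pearson's chi-square test. No denominator is given.

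**General rules.** SAP 8 places efficacy analyses on the FAS unless specified otherwise. Protocol 9.3.5 says that, by default, "descriptive summaries will be based on observed cases", and leaves further missing-data detail to the SAP.

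**LOCF.** Protocol 9.3.6.1, on the primary endpoint: "Analysis of covariance (ANCOVA) with missing data imputed by an LOCF approach will be used as sensitivity analyses". Protocol 9.3.5 says that missing IOP "may be imputed using the last-observation-carried-forward (LOCF) approach for sensitivity analyses". In SAP 8.1.2, "the sensitivity analysis will be performed using the same MMRM model on PPS"; nothing else is listed and no reason is given.

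**The concern.** A subject who needed added IOP-lowering therapy has not shown a response to the assigned regimen. If that subject's later IOP is set to missing and nothing else is said, the subject has no response status at that visit. An observed-case rate then leaves the subject out of both numerator and denominator. The MMRM can still use the subject's other visit under a missing-at-random assumption; a chi-square test at a single visit cannot.

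Two things are at stake. The first is an inflated responder rate in any arm that has such subjects, with a between-arm difference that can move in either direction. The second is that two programmers could produce different tables from the same SAP. Settling the rule after unmasking would be a post-hoc choice that can change a p-value.

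**Working it through.** **1. The plan's own figure.** The documents give no responder rate and no rate of added therapy. The only related figure is the power statement in Protocol 9.2 and SAP 3.3: 50 per arm, 2.0 mmHg, SD 3.5 mmHg, two-sided 5%, about 80%. The standard error is 3.5 × √(2/50) = 0.70, so 2.0/0.70 = 2.857. Power is Φ(2.857 − 1.960) = 81.5%, or 80.8% with the noncentral t on 98 df. The figure reproduces and is not in dispute. It supplies the 50 per arm used below.

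**2. Who is affected.** Censoring applies only to IOP collected after the therapy. A subject treated after Week 2 still counts at Week 2. SAP 4.1.4 maps Days 2–28 to Week 2 and Days 29–57 to Week 6, so exit readings taken on Day 29 or later but before any added therapy still supply a Week 6 value. The subjects at issue are those with no uncensored study-eye IOP for the visit.

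**3. Effect on one arm's rate.** With x responders of n and d non-responders dropped, the rise is x/(n − d) − x/n.

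- 40%: 20/48 − 20/50 = 1.7 points; 20/46 − 20/50 = 3.5 points
- 60%: 30/48 − 30/50 = 2.5 points; 30/46 − 30/50 = 5.2 points

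**4. Effect on the difference.** From 20/50 v 30/50, a difference of 20.0 points:

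- 4 QD dropped: 65 is not reached in BID, so 60.0 − 43.5 = 16.5
- 4 BID dropped: 65.2 − 40.0 = 25.2
- 4 dropped in each arm: 65.2 − 43.5 = 21.7

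**5. Effect on the test.** The uncorrected Pearson chi-square equals z², with z = (p₂ − p₁)/√[p(1 − p)(1/n₁ + 1/n₂)] and p the pooled rate. For 20/50 v 30/50, z = 0.20/√(0.25 × 0.04) = 2.00, p = 0.0455. For 20/46 v 30/50, the pooled rate is 50/96 and z = 0.1652/0.1021 = 1.62, p = 0.1055. All counts are assumptions.

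| Responders QD v BID, of 50 each | p, kept as non-responders | Dropped | p, dropped |
|---|---|---|---|
| 20 v 30 | 0.0455 | 1 QD | 0.0563 |
| 20 v 30 | 0.0455 | 2 QD | 0.0695 |
| 20 v 30 | 0.0455 | 4 QD | 0.1055 |
| 20 v 30 | 0.0455 | 4 QD and 4 BID | 0.0363 |
| 15 v 25 | 0.0412 | 2 QD | 0.0590 |
| 15 v 25 | 0.0412 | 4 QD | 0.0842 |
| 20 v 28 | 0.1093 | 4 BID | 0.0411 |
| 20 v 32 | 0.0163 | 4 QD | 0.0438 |
| 15 v 30 | 0.0026 | 4 QD | 0.0072 |
| 18 v 24 | 0.2241 | 4 QD | 0.3815 |

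The first seven rows start near 0.05, and six of them cross it, one in the opposite direction. The last three start further away and do not cross.

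**6. Primary analysis.** A large-sample simulation (600,000 per arm) used the model of SAP 12.1 with a true difference of −2.0 mmHg, SD 3.5, one common correlation between readings, and Week 6 removed when a trigger reading was high. When the observed Week 2 IOP is the trigger, the bias is within 0.002 mmHg of zero. When an unscheduled reading is the trigger and 4.0% to 13.5% of QD subjects are censored, the difference shrinks by 0.02 to 0.09 mmHg across correlations 0.4 to 0.8. These censoring rates are also assumptions.

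**The case against.** **Exclusion is inferred.** A reader might take the SAP to order exclusion. It does not. SAP 8 puts efficacy analyses on the FAS, which could mean that all FAS subjects stay in the denominator, and the Protocol's observed-case default covers descriptive summaries without mentioning the test. This stands as a limit on the wording. It does not remove the gap, because the FAS rule says who is analysed, not how a subject without a value is classified.

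**Few subjects.** Ocular hypotensives are prohibited, with safety as the governing consideration for any exception (Protocol 6.6.1), and withdrawal is expected to be uncommon (Protocol 7.2). Protocol 7.2.1 gives IOP above 34 mmHg as an example of lack of efficacy. With SD 3.5 and an assumed QD on-treatment mean of 20, 22 or 24 mmHg, one study-eye reading exceeds 34 with probability of about 0.003%, 0.03% or 0.2%. Investigators may act at lower values, so this is not a bound, but nothing in the documents supports a large group. This stands.

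**No stated claim depends on it.** Superiority rests on IOP at six time points (SAP 6.4). The responder tests are secondary and unadjusted: four definitions at two visits. This also stands, and it limits the weight of the point.

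**A simple failure rule is incomplete.** SAP 6.2.1 is not limited to the study eye, so therapy in the fellow eye alone could turn a study-eye responder into a failure. A subject withdrawn for lack of efficacy without added therapy would still disappear. Both are fair, and the fix below covers them.

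**Conclusion.** The point holds as a gap in the secondary responder analysis. As written, the natural reading removes subjects with censored IOP and inflates the affected arm's rate: by 1.7 to 5.2 points when 2 or 4 of 50 are dropped, at base rates of 40% or 60%. The between-arm difference can move either way, and a changed conclusion needs a borderline result. These sizes rest on assumed counts.

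Two stronger readings are tempting, and the documents do not support them. One is that the primary comparison is compromised: under the assumptions tried, the attenuation is at most 0.09 mmHg against a planned 2.0 mmHg, so any bias is likely negligible. The other is that the SAP breaks a firm commitment to LOCF-ANCOVA and must restore it. Protocol 9.3.6.1 is firm, but Protocol 9.3.5 is permissive and defers detail to the SAP. For continuous secondary endpoints the Protocol offers MMRM or LOCF-ANCOVA, so there is no mismatch there. What remains is a minor, unexplained difference on the primary endpoint's sensitivity analysis. The PPS analysis changes the population, not the missing-data assumption.

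**What to change.** **SAP 8.2, before unmasking:**

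- Keep all FAS subjects in the denominator of each responder rate and chi-square test.
- Count a subject as a non-responder at each analysis visit where study-eye IOP is unavailable for either of two reasons: censoring under SAP 6.2.1 for therapy that could affect the study eye, or withdrawal for lack of efficacy.
- State how subjects missing for other reasons are counted, and report their number per arm.

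The cost is slightly lower responder rates in an arm with such subjects, one paragraph of SAP text and minor programming.

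**Separately, and minor:** reconcile Protocol 9.3.6.1 and 9.3.5 with SAP 8.1.2 on LOCF-ANCOVA, and document the reason for any change. If the analysis is not reinstated, this costs a sentence.
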